7.8 Long term follow-up assessments

Participants will be followed up 10 (to 14) days after the second endotoxin injection day (Period 2, Day 21) by telephone. Any new adverse events will be recorded. Participants will be thanked for their involvement in the study and arrangements made to provide the monetary reimbursement due to them. In the event of a participant remaining uncontactable at the end of the follow up window, we will interrogate the hospital records of the participant to clarify vital status and any evidence of untoward events. Participants will be declared 'lost to follow up' if they are uncontactable 28 days after the second endotoxin injection day. A file note will be made in this instance.

7.9 Qualitative assessments

Not applicable to this study

7.10 Withdrawal or postponement criteria

Subjects may be withdrawn or may discontinue from the trial if the following occur:

- Inability to insert intravenous cannula and/or obtain venous blood samples
- Withdrawal of consent
- Development of an intolerable adverse event due to study participation as determined by the investigator and/or subject
- Development of an intercurrent illness, condition or procedural complication that would interfere with the subject's continued participation, unless further study activities can be appropriately postponed (see section 7.10.1)
- At the time of planned endotoxin injection, receipt of a non-study medication in the preceding 48 hours that, in the opinion of the investigator, is likely to affect inflammation, thrombosis or haemostasis, unless the endotoxin injection visit can be appropriately postponed (see section 7.10.1)
- Poor compliance (<80% of doses taken) with study aspirin (aspirin lysine) during the preceding medication period, unless the endotoxin visit can be appropriately postponed (see section 7.10.1) to achieve 80 % compliance
- Violation of the protocol
- The investigator feels it is medically in the best interest of the subject to discontinue the subject's participation in the study
- Previously unknown data becoming available raising concern about the safety of the study drugs, so that continuation could cause potential risks to the subjects

The reason for withdrawal/discontinuation will be documented in the Case Report Form (CRF).

Withdrawn participants who receive at least one dose of IMP or endotoxin will be followed up by telephone at 10-14 days after withdrawal, and additionally all who discontinue due to adverse events (AEs) will be followed up until resolution or stabilisation. All outcomes of AEs will be recorded in the CRF.

Withdrawn participants who have proceeded to randomisation will not be replaced.

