7.3 The randomisation scheme

Participants will be randomised to one of the following eight treatment sequences, in a 1:1:1:1:1:1:1:1 fashion:

- No IMP for 10-14 days, then \geq 5 week washout period, then no aspirin for 10-14 days, but a loading dose of ticagrelor (180 mg) given one hour before endotoxin injection (sequence 1).
- No aspirin for 10-14 days, but a loading dose of ticagrelor (180 mg) given one hour before endotoxin injection, then \geq 5 week washout period, then no IMP for 10-14 days (sequence 2).
- Aspirin (aspirin lysine) 20 mg BD for 10-14 days, then \geq 5 week washout period, then aspirin (aspirin lysine) 20 mg BD for 10-14 days plus a loading dose of ticagrelor (180 mg) given one hour before endotoxin injection (sequence 3).

- Aspirin (aspirin lysine) 20 mg BD for 10-14 days plus a loading dose of ticagrelor (180 mg) given one hour before endotoxin injection, then \geq 5 week washout period, then aspirin (aspirin lysine) 20 mg BD for 10-14 days (sequence 4).
- Aspirin (aspirin lysine) 75 mg OD for 10-14 days, then \geq 5 week washout period, then aspirin (aspirin lysine) 75 mg OD for 10-14 days plus a loading dose of ticagrelor (180 mg) given one hour before endotoxin injection.
- Aspirin (aspirin lysine) 75 mg OD for 10-14 days plus a loading dose of ticagrelor (180 mg) given one hour before endotoxin injection, then \geq 5 week washout period, then aspirin (aspirin lysine) 75 mg OD for 10-14 days (sequence 6).
- Aspirin (aspirin lysine) 300 mg OD for 10-14 days, then \geq 5 week washout period, then aspirin (aspirin lysine) 300 mg OD for 10-14 days plus a loading dose of ticagrelor (180 mg) given one hour before endotoxin injection (sequence 7).
- Aspirin (aspirin lysine) 300 mg OD for 10-14 days plus a loading dose of ticagrelor (180 mg) given one hour before endotoxin injection, then \geq 5 week washout period, then aspirin (aspirin lysine) 300 mg OD for 10-14 days (sequence 8).

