9.2 Operational definitions for (S)AEs

Adverse events and reactions will be recorded and reported from randomisation to 10 days after visit 3 (first endotoxin injection day), and from visit 6 (start of period 2) to 10 days after visit 7 (second endotoxin injection day). Thus, adverse events occurring in the break between the first and second medication periods, excepting those originating in the 10 days after endotoxin injection, will not be recorded or reported.

All SAEs will be reported to the sponsor within 24 hours of the research team becoming aware of them. This will be using the sponsor's proforma which will be sent by email to a dedicated address provided

specifically for this purpose. A copy will be kept in the trial master file and the AE log will be completed. All SAEs will be reviewed at the regular trial management group meetings.

All other AEs not meeting the criteria for reporting as serious will be recorded in the CRF, with the exception of the following events which will not be reported, as they can be expected as a normal response to endotoxin:

- Abnormal body temperature, excepting if $>39^{\circ}\text{C}$ and $<34^{\circ}\text{C}$, unless this persists at 6 hours post-endotoxin or meets the criteria for reporting as an SAE.
- Change in pulse rate, excepting pulse rates of >140 bpm and <45 bpm or if meeting the criteria for SAE reporting.
- Change (increase or decrease) in systolic or diastolic blood pressure from baseline of <40 mmHg unless meeting the criteria for SAE reporting.
- Self-limiting symptoms wholly due to endotoxaemia, for example fever, rigors, general malaise, nausea, vomiting or headache, at the discretion of the investigator, unless meeting the criteria for SAE reporting.
- Alterations in leukocyte (or subset) counts, platelet count or C-reactive protein unless meeting the criteria for SAE reporting.

The investigators will assess the relatedness of adverse events to the IMPs (aspirin [aspirin lysine], ticagrelor) and NIMP (endotoxin).

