9.3 Recording and reporting of SAEs, SARs AND SUSARs

SAEs/SUSARs will be recorded and reported from randomisation to 10 days after visit 3 (first endotoxin injection day), and from visit 6 (start of period 2) to 10 days after visit 7 (second endotoxin injection day). Thus, adverse events occurring in the break between the first and second medication periods, excepting those originating in the 10 days after endotoxin injection, will not be recorded or reported.

These must be recorded on the Sheffield Teaching Hospitals NHS Foundation Trust SAE reporting Form and emailed to the Sponsor's dedicated email address for this purpose **within 24 hours** of the research staff becoming aware of the event.

For each **SAE or SUSAR** the following information will be collected:

- full details in medical terms and case description
- event duration (start and end dates, if applicable)
- action taken
- outcome
- seriousness criteria
- causality (i.e. relatedness to trial drug / investigation), in the opinion of the investigator
- whether the event would be considered anticipated.

Any change of condition or other follow-up information should be emailed to the Sponsor as soon as it is available or at least within 24 hours of the information becoming available. Events will be followed up until the event has resolved or a final outcome has been reached.

All SAEs assigned by the PI or delegate as both suspected to be related to IMP-treatment and unexpected will be classified as SUSARs and will be subject to expedited reporting to the Medicines

and Healthcare Products Regulatory Agency (MHRA). The sponsor will inform the MHRA, the REC and the relevant Marketing Authorisation Holder(s) of SUSARs within the required expedited reporting timescales.

SAEs related to the NIMP (endotoxin) will be reported by the investigators to the sponsor, but further forwarding to other agencies will not be required, as per European Directive 2011/C 172/01. NIMP-related SAEs will be evaluated by the sponsor and investigator team with regard to ongoing safety implications. If there are ongoing safety implications for the trial then these will be addressed via urgent safety measure, substantial amendment or termination of the trial.

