10.7 Participant population

- The pharmacodynamic analysis set will include all participants who achieve at least 80% compliance with study medication during each of the two periods and who complete both endotoxin injection days.
- The safety analysis set (for the purposes of adverse event reporting etc.) will include any participant randomised into the trial that received at least one dose of trial drug or one dose of intravenous endotoxin.

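### The safety set starts at first dose, so controls who withdraw before the first endotoxin day drop out of the adverse-event tables while comparable aspirin participants are counted

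*Protocol*

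**What the plan says.** **Safety set.** Protocol 10.7 and SAP 10.7 give the same rule. The set, meant for adverse-event reporting, comprises "any participant randomised into the trial that received at least one dose of trial drug or one dose of intravenous endotoxin".

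**First exposure.** Under Protocol 7.7, period 1 medication starts on Day 1 and the first endotoxin day (visit 3) is Day 11 to 15. Under 7.3, controls take nothing in the meantime. Sequence 1 has no IMP in period 1, so its first exposure is the endotoxin itself. Sequence 2 has the ticagrelor control regimen first: "no aspirin for 10-14 days, but a loading dose of ticagrelor (180 mg) given one hour before endotoxin injection".

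**Event collection.** Protocol 9.2 makes no distinction by arm: "Adverse events and reactions will be recorded and reported from randomisation to 10 days after visit 3". Section 9.3 applies the same window to SAEs and SUSARs. The definition of an adverse event in 9.1, however, is limited to a participant who has been given a medicinal product.

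**Withdrawal.** Protocol 7.10 says "Withdrawn participants who receive at least one dose of IMP or endotoxin will be followed up by telephone at 10-14 days after withdrawal". The sentence then continues: "additionally all who discontinue due to adverse events (AEs) will be followed up until resolution or stabilisation". It is followed by: "All outcomes of AEs will be recorded in the CRF". The last two carry no dose condition.

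**The concern.** A safety set that starts at first dose works when every arm is dosed at about the same time. Here one arm is untreated by design for the first 10 to 14 days, so the same rule opens the set at different times in different arms. Withdrawal in that interval does not need a drug. Section 7.10 allows it for intercurrent illness, procedural complications or interfering medication, and all participants have blood sampling and a bleeding time at visit 2.

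What is at stake is the adverse-event table for aspirin against no aspirin. In period 1, the number of event-related withdrawals before the first challenge is zero among safety-set controls whatever happens, but it can be above zero in each aspirin arm. Treatment is open-label and the control group is the only one without aspirin, so its event count should not depend on whether a participant reached the challenge. Data already recorded would be left out of the table by definition.

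**Working it through.** **1. The plan's own group size.** Protocol 10.1 gives D² = 0.1828, 4 groups, alpha 0.05 and 16 per group. A noncentral F calculation with λ = 4 × 16 × 0.1828 = 11.70 gives power 0.802, as stated. Allowing for 10% drop-out, 16 / 0.9 = 17.8, rounded up to 18 per group, and 4 × 18 = 72. Both figures reproduce. Two of the eight sequences are control, so 72 × 2/8 = 18 controls are expected. Section 7.3.1 specifies simple randomisation, so 18 is an expectation; the central 95% binomial range is 11 to 25.

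**2. The provisions side by side.**

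| | Aspirin arms | Control (sequences 1, 2) |
|---|---|---|
| Events recorded from (9.2, 9.3) | Randomisation, Day 0 | Randomisation, Day 0 |
| First dose of drug or endotoxin (7.3, 7.7) | Day 1 | Visit 3, Day 11 to 15 |
| Withdrawn with an event between Day 1 dose and visit 3: in safety set (10.7)? | Yes | No |
| Followed to resolution or stabilisation (7.10)? | Yes | Yes |
| Routine 10-14 day call after withdrawal (7.10)? | Yes | No |

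The gap in entry is 10 to 14 days, or 18 × 10 = 180 to 18 × 14 = 252 control person-days. Controls who reach visit 3 enter the set, and nothing in 10.7 removes their earlier events. By period 2 every continuing control has had endotoxin, so the asymmetry is confined to period 1. An aspirin participant who withdraws between randomisation and the first dose is also excluded, but that window is about one day.

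**3. How many controls could be left out.** Let s be the share of the 10% drop-out that falls before visit 3. The documents do not give s, so the whole range is shown. Expected controls left out = 18 × 0.10 × s. Chance of at least one = 1 − (1 − 0.10s)^18. The last column assumes that half of these withdraw because of an event, which the documents also do not give: 18 × 0.10 × s × 0.5.

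| s | Controls left out | Chance of at least one | Of these, with an event |
|---|---|---|---|
| 0 | 0 | 0% | 0 |
| 0.25 | 0.45 | 37% | 0.225 |
| 0.50 | 0.90 | 60% | 0.45 |
| 0.75 | 1.35 | 75% | 0.675 |
| 1 | 1.80 | 85% | 0.90 |

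The bottom row places the whole drop-out allowance for a two-period study before the first challenge, so it is an upper bound on the plan's own allowance.

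**4. Direction.** Leaving these controls out lowers the control event rate only if events are more common among them than among the controls who stay. That is likely when events are a reason for leaving, but it is not certain.

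**The case against.** The strongest reply has four parts.

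*These controls are followed up.* A reader who stops at the dose condition in 7.10 might infer that a control withdrawn for an adverse event before visit 3 gets no follow-up. The documents do not support that. The rest of the sentence covers everyone who discontinues because of an adverse event, without a dose condition, and for longer than a single call. Only undosed participants who leave for other reasons miss the routine call. This part stands in full, subject to the doubt that the 9.1 definition creates if read literally.

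*The events are captured.* Collection starts at randomisation, SAEs go to the sponsor within 24 hours, reasons for withdrawal go in the CRF, and a CONSORT diagram is planned. This also stands. The omission is from tables built on the safety set, not from the data.

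*No planned comparison is biased.* Safety is not among the objectives or endpoints in section 3, and neither 10.3 nor 10.6 contains a between-arm test of adverse events. This stands. A reader might still convert the exclusion into a percentage excess of events on aspirin. With an assumed true rate of 15%, 10% of controls leaving early and half of those because of an event, the control rate would be (0.15 − 0.05) / 0.90 = 11.1%. But none of these inputs is in the documents, and they imply that one third of all events (5 of 15 points) end in withdrawal within about two weeks. Section 7.10.1 also allows postponement or restart for intercurrent illness, which works against that. The participant count is the defensible measure.

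*An exposure-based safety set is legitimate.* In general it is, and it fits the 9.1 definition. It fits less well with an arm that is unexposed by design and with collection from randomisation. This part does not remove the point.

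**Conclusion.** The point holds as a narrow one about the analysis set. Section 10.7 excludes controls who withdraw before the first challenge and includes aspirin participants withdrawn after Day 1 for the same reason, although events are collected from randomisation in both. Event-related withdrawal before the first challenge is therefore zero among safety-set controls by construction.

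The expected size is 0 to 1.8 of about 18 controls, and fewer than one with an event. This rests on the plan's ceiling of 10% drop-out and on two assumptions: the share of drop-outs before visit 3 (0 to 100%) and half of those being event-related. No primary or secondary endpoint and no planned test changes. It is worth correcting because the exclusion depends on arm and the correction is almost free, not because a material distortion has been shown.

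A separate drafting conflict remains. Read literally, 9.1 does not allow an unexposed control to have an adverse event, while 9.2 and 9.3 collect events from such a control from Day 0.

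**What to change.** - In Protocol 10.7 and SAP 10.7, define the safety set as all randomised participants. Count events from randomisation in period 1 and from visit 6 in period 2, by allocated regimen, with no IMP as one of the regimens.
- If the sponsor prefers to keep an exposure-based set, at minimum report events and withdrawals in controls before first exposure alongside the safety tables.
- Reconcile the adverse-event definition in 9.1 with the collection window in 9.2 and 9.3, so that it is clear that an event in a not-yet-exposed control is an adverse event for this trial.

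This point does not require changes to the follow-up wording in 7.10, 8.9 or 8.10. The cost is a few lines in two documents, with no new data collection, because these events are already to be recorded.

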7.10.1 Provision for postponement of visit in the event of intercurrent illness

In the event of the following occurring in relation to a study participant:

- an intercurrent illness, for example a viral upper respiratory tract infection;
- requirement for a course of medication that, in the opinion of the investigators, is likely to affect measures of inflammation, thrombosis or haemostasis; or
- compliance with aspirin (aspirin lysine) is <80% during the preceding study medication period

then if the subsequent endotoxin injection visit cannot be postponed to a time within the permitted window of 10-14 days into the medication period at which the illness or relevant effect of medication has deemed to have resolved or compliance has increased to at least 80% for the medication period, study medication may be stopped and the medication period restarted once the intercurrent illness or requirement for medication is deemed to have resolved, or when compliance is likely to be at least 80%. In this instance, an unscheduled visit will be arranged, the existing supply of aspirin (aspirin lysine) will be collected from the participant and returned to pharmacy for counting and destruction, and a new supply of aspirin (aspirin lysine) will be issued, dispensed after study-specific prescription request has been made to the pharmacy at the Northern General Hospital. A file note will be made in the TMF.

7.11 Storage and analysis of clinical samples

The samples will be stored and analysed according to the study-specific laboratory manual.

7.12 End of study

The study will end when the last laboratory analyses are completed. The sponsor will notify the MHRA of the end of the study within 90 days of its completion. In the event of early termination, this will be reported within 15 days.

8 STUDY MEDICATIONS

8.1 Name and description of investigational medicinal product(s)

The following medications will be used for experimental purposes during the study:

- Aspirin lysine (e.g. 'Asperic' [Sanofi-Aventis] or 'Cardirene' [Sanofi-Aventis] '100 mg' sachets)
 - Each aspirin lysine '100 mg' sachet contains 180 mg aspirin lysine, equivalent to 100 mg acetylsalicylic acid (aspirin). In this protocol the stated dose refers to the aspirin content.
 - Participants will be asked to prepare doses of 20 mg twice daily orally, where directed by the protocol, by dissolving 100 mg (1 sachet) in 100ml of drinking water and ingesting 20 ml of the solution using a graduated syringe, discarding the remainder.

- Participants will be asked to prepare doses of 75 mg once daily orally, where directed by the protocol, by dissolving 100 mg (1 sachet) in 100 ml of drinking water, removing 25 ml of the solution using a graduated syringe, and ingesting the remainder.
- Participants will be asked to prepare doses of 300 mg once daily orally, where directed by the protocol, by dissolving 300 mg (3 sachets) in 100 ml of drinking water and ingesting the solution.
- A new sachet (or sachets) will be used for each dose of study medication
- Ticagrelor 90 mg oro-dispersible tablets (AstraZeneca, 10 tablets per pack)
 - Participants will be asked to take a loading dose of 180 mg (two orodispersible 90 mg tablets) 1 hour before endotoxin injection where specified by the randomisation allocation. This will be directly observed by the research team.

8.2 Regulatory status of the drug

- Aspirin (aspirin lysine) 100 mg sachets are not licensed in the UK but are licensed in other EU countries (e.g. Belgium, Italy) for the purposes of analgesia and antipyresis. Other preparations of aspirin are licensed in the UK for similar indications, as well as an antithrombotic agent after ACS.
- As there is no marketing authorisation in the UK for aspirin lysine, we will import this from another EU country facilitated by an existing relationship with Mawdsleys Ltd.
- Ticagrelor 90 mg orodispersible tablets are licensed in the UK, in combination with aspirin, for the treatment of ACS.
- We will retain the original presentation of drugs as supplied without modification, but will be asking participants to vary the doses of aspirin (aspirin lysine) as detailed elsewhere in this protocol.

8.3 Product Characteristics

Aspirin (aspirin lysine) 100 mg sachets have a current summary of product characteristics (SmPC) that has been translated and notarised from the original French. A copy will be kept in the trial management file.

The current version of the SmPC for ticagrelor 90 mg orodispersible tablets will also be available for reference in the trial management file.

The study team will check for updates to these documents at regular intervals throughout the development and conduct of the study, and will review and file these as needed, if necessary obtaining further notarised translations. If an update to section 4.8 (the reference safety information) is involved, the revised SmPC will be submitted and approved as a substantial amendment before the revised SmPC is filed as the new reference safety information for the trial for the assessment of expectedness of adverse events.

8.4 Drug storage and supply

Aspirin (aspirin lysine) 100 mg sachets will be sourced by the Northern General Hospital Pharmacy through a study-specific arrangement with Mawdsleys Ltd at market price.

Ticagrelor 90 mg orodispersible tablets will be sourced by the Northern General Hospital Pharmacy locally at market price.

The initial shipment will be requested on site initiation (manual ordering) and re-ordering will occur manually as necessary until the end of the study.

Prior to study medication dispensing, all study medications will be kept in a secure location in the pharmacy at Northern General Hospital, Sheffield, under appropriate storage conditions with temperature excursions permitted between 15°C and 30°C. Both aspirin (aspirin lysine) and ticagrelor will be segregated as clinical trial stock for the purposes of this study.

Aspirin (aspirin lysine) will be supplied to the investigators upon receipt of a suitable signed study-specific prescription at the start of each period. Only medically-qualified members of the study team will be able to complete the prescription. Where participants are required to take aspirin (aspirin lysine) by the randomisation allocation, one box of 30 sachets will be dispensed per period for each participant randomised to receive either aspirin 20 mg BD or aspirin 75 mg OD and two boxes of 30 sachets will be dispensed per period for each participant randomised to receive aspirin 300 mg OD.

Packs of ten 90 mg oro-dispersible ticagrelor tablets will be dispensed from the pharmacy to the investigators, on request, for storage in a dedicated area within the NGH-CRF. The pack will then be split and used to administer doses to a number of participants. Prescription, which will only be able to be made by a medically-qualified member of the study team, and administration will be recorded on a Sheffield Teaching Hospitals Drug Administration Record. A drug accountability log and temperature monitoring records will be kept for the ticagrelor stored in the NGH-CRF.

There are no specific post-dispensing storage instructions.

Unused medication and used packaging will be returned to pharmacy at the end of each treatment period, who will perform pill/sachet count for accountability and will supervise destruction.

In the event of postponing visit 3 or 7 because of intercurrent illness and restarting a medication period from the beginning, unused medication from the period prior to the postponement will be returned to pharmacy and a new study-specific prescription will be made by a medically-qualified investigator for a new supply of aspirin (aspirin lysine).

